COVER PAGE

Official title: Severity and time course of GCX damage in critically ill patients

NTC number: NCT03146585

Date of the document: 7. 11. 2019

Objective: Endothelial glycocalyx (EG) plays central role in coupling functions of microcirculation and tissue metabolism. EG is particularly important in critically ill patients when it gets damaged. The aim of study was to describe the condition of EG in critically ill patients by non-invasive method in dependence of severity of the illness and usage of methods of organ support.

Design: monocentric, prospective observational study.

Setting: Intensive Care Unit (ICU), University Hospital.

Methods: Adult patients admitted to the ICU with anticipated length of stay at least 7 days were enrolled. Demographic and clinical data were recorded together with sublingual microcirculation recordings for Perfused Boundary Region (PBR) analysis.

Scientific background: Endothelial glycocalyx (EG) is a microscopic lining of the inner surface of blood vessels. The results of recent research have shown a central role of EG in the physiological and pathophysiological processes of microcirculation and in the development of endothelial damage. EG mucopolysaccharide structure makes it susceptible to degradation, which occurs most often in the context of critically ill patients with sepsis, trauma and ischemia-reperfusion injury. Clinical studies on the dynamics of EG changes in intensive care patients are rare, and we have not found work on the impact of organ support techniques in available resources. The most data are from the area of extracorporeal circulation in cardio surgery. Given the current evidence of EG degradation in critical conditions, we hypothesized that there is a relationship between the degree of EG degradation and the severity of the clinical condition.

Statistical considerations: The calculation of the minimum sample size of 30 patients was based on the assumption of a difference in Perfused Boundary Region values as an indirect indicator of EG damage (detailed description of the methodology below) between healthy volunteers and patients in critical condition. correlation coefficient 0.6), defining type I error = 0.05 and study strength = 0.9. The differences between groups were calculated by type of data, compared with an unpaired t-test, Mann Whitney's rank test, and One-Way ANOVA. The Pearson correlation coefficient with a 95% confidence interval was used to assess the correlation between PBR and APACHE II, SOFA and fluid balance. To assess the ability of PBRs (sensitivity and specificity) to predict septic shock or positive fluid balance, the Receiver Operating Characteristic (ROC) curve was calculated. Differences with $P < 0.05$ were considered statistically significant. Statistical analyzes and graphs were performed using MedCalc 7.6.0 computer programs. (MedCalc Software, Ostend, Belgium) or Prism 5 for Mac OS X (Version 5, Dec. 19, 2008).

Chief Investigator: [name]

Sponsor Number: AZVCR 15-3881/A, all rights reserved.

Name of site: Hradec Kralove

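### Does sizing the study on a volunteer-versus-patient PBR difference leave its organ-support comparisons underpowered in a way that the plan must correct?

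*Combined protocol and SAP*

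**What the plan says.** The Objective sets out to describe the glycocalyx "in dependence of severity of the illness and usage of methods of organ support". Scientific background adds, on the second of these, that "we have not found work on the impact of organ support techniques in available resources"; the hypothesis it then states concerns severity alone.

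Statistical considerations opens with the sample size: "The calculation of the minimum sample size of 30 patients was based on the assumption of a difference in Perfused Boundary Region values", taken "between healthy volunteers and patients in critical condition". The text then breaks off and resumes with a stray correlation coefficient of 0.6, a type I error of 0.05 and power of 0.9.

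Three kinds of analysis follow:

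- Group comparisons: "The differences between groups were calculated by type of data, compared with an unpaired t-test", a Mann-Whitney test or one-way ANOVA. The groups are not named.
- Correlation: "The Pearson correlation coefficient with a 95% confidence interval was used to assess the correlation between PBR and APACHE II, SOFA and fluid balance".
- ROC curves for the ability of PBR "to predict septic shock or positive fluid balance".

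Differences with P below 0.05 "were considered statistically significant". Organ support is not mentioned in this section.

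**The concern.** The aim has two strands, and the readable sizing statement serves neither directly. Severity at least has a named analysis with an interval. Organ support appears in neither the correlation list nor the ROC list, so only the generic group tests could address it. Those tests would divide the patients into subsets, and so have less power than a contrast that sets all of them against volunteers.

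Two misreadings would be possible. A comparison that misses P < 0.05 could be taken to show that organ support makes no difference, when the study could not have seen a moderate one. A comparison that reaches P < 0.05 could exaggerate the effect. Since the authors found no earlier work on the question, a reader would have little to check either result against.

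**Working it through.** **The plan's own figure.** The readable inputs are r = 0.6, alpha 0.05 (taken as two-sided) and power 0.9. For a correlation, n = ((1.960 + 1.282)/atanh(0.6))² + 3 = (3.242/0.693)² + 3 = 24.9, so 25. This is not 30; an unstated 15% dropout allowance would take 25 to 30 (25/0.85 = 29.4). The volunteer contrast cannot be checked, because no difference, SD or number of volunteers is readable. As the sentence is broken in the available text, the mismatch is not evidence of an error. At n = 30 the power for r = 0.6 is Φ(0.693 × √27 − 1.960) = Φ(1.64) = 95%.

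**Organ-support comparison at 30 patients.** Assumptions, none of them in the document: two groups, one PBR value per patient, two-sided 0.05, differences in between-patient SD units, and the splits shown. Power comes from the noncentral t with 28 df and noncentrality d × √(n1·n2/30). At 15/15 and d = 0.8 this is 0.8 × √7.5 = 2.19. The 95% CI half-width is 2.048 × √(1/n1 + 1/n2).

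| Split | Power, 0.5 SD | Power, 0.8 SD | Power, 1.0 SD | Power, 1.5 SD | Difference for 90% power | CI half-width |
|---|---|---|---|---|---|---|
| 15/15 | 26% | 56% | 75% | 98% | 1.23 SD | 0.75 SD |
| 10/20 | 24% | 51% | 70% | 96% | 1.30 SD | 0.79 SD |
| 6/24 | 18.5% | 39.5% | 56% | 89% | 1.53 SD | 0.93 SD |

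**How far this depends on the assumptions.**

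- *Effect size.* The document's only readable effect is r = 0.6. As a two-group difference at 15/15 it is 2 × 0.6/√(1 − 0.36) = 1.5 SD, with 98% power. That fragment is not an organ-support effect, but 0.8 SD has no source in the document either.
- *Number of patients.* Thirty is a minimum. For 0.8 SD, power is 79% at 25/25 and 86% at 30/30.
- *Sidedness.* A one-sided test at 15/15 would have 69% power for 0.8 SD.

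**Does the text contain the faulty rule?** The sentence on significance says which differences count as significant. It does not say that the others are evidence of no association. The group sentence says differences are calculated, so an estimate is planned and only its interval goes unmentioned.

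**What an interval would gain.** In simulation at 15/15 with a true difference of 0.5 SD, significant estimates average 0.93 SD. Among those significant results the 95% interval covers the truth about 90% of the time. An interval helps a reader judge a null result but does not remove exaggeration in a significant one.

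**The case for a change.** The strongest reply is that the CI half-width needs no assumed effect. At 15/15, an observed difference of zero would still be compatible with about 0.75 SD either way, and a bare P value hides that. A descriptive aim calls for estimates with their precision, and the severity correlations get an interval while group differences do not. Further, if the group tests are not meant for organ support, then no listed analysis addresses that part of the aim, which would be a larger gap.

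The half-width argument stands as arithmetic, and an interval on each group difference would be good reporting. It does not show that anything planned is wrong, because the interval follows from the same data and the same tests. The argument from elimination has a limit. The sizing sentence is broken, and the section points to a fuller methods description that the available text does not contain. Groups may be named there, so their absence here cannot be held against the plan. A severity-only hypothesis also makes it ordinary to leave the organ-support strand unsized in an observational study.

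**Conclusion.** No change follows. Organ support is in the aim, and no readable sizing input or named analysis refers to it. At exactly 30 patients a two-group comparison would be imprecise: half-width 0.75 to 0.93 SD, and power of 56% down to 40% for 0.8 SD across splits from 15/15 to 6/24. These figures rest on a chosen effect size, assumed splits, a two-sided test, one value per patient, the stated minimum as the actual enrolment, and tests matched to organ support by inference. They contradict no stated figure, since the 0.9 is never claimed for organ support. They expose no faulty rule, since nothing tells the analyst to read non-significance as absence of an association.

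The remaining gap is one that analysts fill sensibly when reporting: say which organ-support groups were compared and how large they were, and give each PBR difference with its 95% interval. That is a minor reporting courtesy and alters no test, sample or result.

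### PBR versus fluid balance is assessed only by an unadjusted Pearson coefficient, which describes the marginal association but cannot show a link beyond shared severity of illness

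*Combined protocol and SAP*

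**What the plan says.** The Design line describes a "monocentric, prospective observational study", so the study does not assign fluids. Under Scientific background the hypothesis is that "we hypothesized that there is a relationship between the degree of EG degradation and the severity of the clinical condition".

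Under Statistical considerations, fluid balance is used twice:

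- As a correlate of PBR: "The Pearson correlation coefficient with a 95% confidence interval was used to assess the correlation between PBR and APACHE II, SOFA and fluid balance".
- As an ROC outcome, with PBR as the predictor: the plan evaluates PBR's ability "to predict septic shock or positive fluid balance, the Receiver Operating Characteristic (ROC) curve was calculated".

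The other methods named are the unpaired t-test, the Mann-Whitney test and one-way ANOVA. No partial correlation, regression model or stratification by severity appears. Differences with P below 0.05 "were considered statistically significant". The documents do not say how fluid balance relates to severity, how fluids are given, or what the PBR–fluid coefficient is meant to show. The stated objective names severity and organ support, not fluids.

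**The concern.** Fluid balance is net intake minus losses. In an observational ICU study it is reasonable to expect that net balance to move with how ill the patient is, through intake, losses or both. The study's hypothesis already supplies the other half of the path, from severity to PBR. If both halves hold, PBR and fluid balance will correlate even when neither has any connection with the other apart from severity.

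What is at stake is interpretation. A significant coefficient could be reported as a specific link between glycocalyx damage and fluid balance, and nothing in the planned analysis would distinguish that from shared severity. The two scores needed to examine the question, APACHE II and SOFA, are already analysed against PBR but are not used here.

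**Working it through.** **Inputs from the plan.** A minimum of 30 patients, type I error 0.05, power 0.9 and a correlation of 0.6 ("correlation coefficient 0.6), defining type I error = 0.05 and study strength = 0.9"). The start of that sentence is missing, so the variables to which 0.6 refers are unknown. The test is taken as two-sided, because sidedness is not stated.

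**Assumed inputs.** PBR–severity correlation a = 0.6 (range 0.4 to 0.7). Fluid–severity correlation b = 0.3 to 0.7, with b = 0 as reference. The documents give neither.

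**The plan's own figure.** For one correlation by Fisher z:

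n = [(1.960 + 1.282) / atanh(0.6)]² + 3 = (3.242 / 0.693)² + 3 = 24.9, so 25.

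This does not reproduce 30. An unstated 15% dropout allowance would (25 / 0.85 = 29.4, so 30). The text bases the figure on a PBR difference between healthy volunteers and patients, but gives no difference or SD, so that route cannot be checked. This is a separate matter; only n = 30 is carried forward.

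**Step 1: smallest significant coefficient at n = 30.** With t(0.975, 28) = 2.048, |r| = 2.048 / √(28 + 2.048²) = 0.361.

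**Step 2: coefficient induced by shared severity.** With no direct link, r(PBR, fluid) = a × b.

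**Step 3: how often P < 0.05 results.** By Fisher z the rate is Φ(√27·atanh(ab) − 1.96) + Φ(−√27·atanh(ab) − 1.96). For b = 0.5: atanh(0.30) = 0.3095, times 5.196 = 1.608; Φ(−0.352) is about 0.36, and the other tail is negligible. A simulation of 100,000 trivariate-normal data sets per row checks this and adds the partial correlation given severity.

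| b (a = 0.6) | Induced r | Crude, Fisher z | Crude, simulated | Partial, simulated |
|---|---|---|---|---|
| 0 | 0 | 5% | 4.9% | 4.9% |
| 0.3 | 0.18 | 16% | 15.9% | 5.1% |
| 0.5 | 0.30 | 36% | 36.9% | 5.0% |
| 0.7 | 0.42 | 64% | 65.7% | 4.8% |

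For a from 0.4 to 0.7 and b from 0.3 to 0.7, the simulated crude rate runs from about 10% to 81%.

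**Step 4: imperfect severity score.** The partial column assumes that severity is measured without error. Suppose instead that the score correlates 0.8 with true severity, with a = 0.6 and b = 0.5. PBR–score is then 0.48 and fluid–score 0.40, so

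partial r = (0.30 − 0.48 × 0.40) / √[(1 − 0.48²)(1 − 0.40²)] = 0.108 / 0.804 = 0.13.

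At n = 30, √26 × atanh(0.134) = 0.69, which gives rejection in about 11% of studies. Adjustment reduces the severity component but need not remove it.

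**Step 5: cost in precision.** On the Fisher z scale the standard error rises from 1/√27 = 0.192 to 1/√26 = 0.196, about 2%. The requirement at r = 0.6 and 90% power rises from 25 to 26. At n = 30, power is 94% for a partial r of 0.6, 80% for 0.5 and 58% for 0.4.

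**The case against.** The best defence is that the plan sets out to describe, and a marginal correlation is a sound answer to a descriptive question. No causal or severity-independent claim about fluids is written anywhere. This stands, and it limits the point to what may be concluded from the coefficient.

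Four stronger readings are tempting, and the documents do not support them:

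- **That the planned test has an inflated type I error.** In the scenarios above, the true marginal correlation is 0.18, 0.30 or 0.42, not zero. Rejecting in 16%, 36% or 64% of studies is power against the null that the Pearson test addresses. The 5% benchmark belongs to a different null, no link beyond severity, which the plan does not state.
- **That the plan treats fluid balance as a severity score, or as a treatment that clinicians set by severity.** The sentence only lists three variables. Nothing in the documents describes how fluids are decided.
- **That the ROC analysis shares the fault.** There PBR is a predictor and positive fluid balance the outcome. For prediction, information that runs through severity still counts.
- **That the adjusted estimate should replace the crude one.** The hypothesis gives no direction. If glycocalyx damage contributes to severity, SOFA is a mediator, and conditioning on it removes part of a real association. An imperfect score also leaves residual confounding, as step 4 shows.

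It is also fair to object that both correlations behind the magnitude are assumed. The figures show what could happen, not what is expected. None of this answers the narrower point: the planned output contains nothing that could support or refute an association beyond severity.

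**Conclusion.** The point holds in a limited form. The unadjusted coefficient is valid as a description but cannot be separated from shared severity, and the plan offers no analysis that addresses the difference. The possible size is material: two severity correlations of 0.6 induce r = 0.36, almost exactly the significance threshold at 30 patients, so about half of such studies (51% in simulation) would report a significant result with no direct link.

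That size depends wholly on an assumed fluid–severity correlation and on an assumed PBR–severity correlation, for which the plan's 0.6 is only a convenient value. With no fluid–severity relation the issue disappears. The PBR–APACHE II and PBR–SOFA analyses, and the severity hypothesis itself, are unaffected. This is a worthwhile, inexpensive addition rather than the correction of a mistake.

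**What to change.** In the Statistical considerations:

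1. Keep the crude PBR–fluid coefficient with its 95% interval, labelled as descriptive and not separable from severity.
2. Beside it, report the partial correlation (or regression slope) of PBR with fluid balance given SOFA, with its 95% interval. Repeat with APACHE II as a sensitivity analysis. State which assessment each variable comes from, since the documents do not give the timing.
3. Claim a PBR–fluid association independent of severity only if the adjusted estimate supports it. Note that adjustment may leave residual confounding or remove a mediated effect.
4. Leave the ROC for positive fluid balance unadjusted, as a prediction analysis.

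The cost is one further analysis, plus its sensitivity version, on variables the plan already analyses. Each adjusted estimate loses one degree of freedom and has an interval about 2% wider on the Fisher z scale. A moderate adjusted association may not be detected with 30 patients, so the interval should carry the interpretation.

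### Does correlating PBR with both APACHE II and SOFA at an unadjusted 0.05, with no primary score named, inflate the false-positive rate enough to need a change?

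*Combined protocol and SAP*

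**What the plan says.** The scientific background on the cover page gives a single hypothesis: "we hypothesized that there is a relationship between the degree of EG degradation and the severity of the clinical condition". It does not define severity. The objective on the same page is descriptive, and the design is a single-centre prospective observational study.

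The statistical considerations turn the hypothesis into an analysis: "The Pearson correlation coefficient with a 95% confidence interval was used to assess the correlation between PBR and APACHE II, SOFA and fluid balance". Two of the three measures are severity scores; fluid balance is not. The same section plans group comparisons and ROC curves, then gives one general threshold: "Differences with $P < 0.05$ were considered statistically significant". The available text has no primary measure, testing order, multiplicity adjustment or exploratory label, and no rule for the case where APACHE II and SOFA disagree.

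The sample-size sentence does not settle the matter. It refers to a PBR difference "between healthy volunteers and patients in critical condition", which is a different question from severity among patients. It then continues, after a visible break, "correlation coefficient 0.6), defining type I error = 0.05 and study strength = 0.9". That correlation is tied to no named score, and the closing bracket has no opening one, so some words before it are missing.

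**The concern.** APACHE II and SOFA are two measures of the same thing. When one hypothesis can be tested in two ways, each at 0.05, and nothing says which counts, an author could report whichever score reaches significance as confirming it. The chance of a spurious confirmation would then exceed the 5% that a reader would take from the stated type I error. If one score were significant and the other not, the plan would not say how to conclude.

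The remedy also looks cheap. Naming one score, or applying Holm across the two, takes a sentence and no extra patients. A plan that states a hypothesis, a type I error and a power invites the question of which test these belong to.

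**Working it through.** **Inputs.** From the statistical considerations: minimum n = 30, type I error 0.05, power 0.9, correlation 0.6, and two severity scores each judged at 0.05. Assumed: two-sided tests (consistent with the 95% interval), and the correlation ρ between APACHE II and SOFA, which the document does not give and which is varied from 0 to 0.9.

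**1. The plan's own figure.** The document states no familywise error rate, so the only figure to reproduce is n = 30. For one correlation by Fisher's z:

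n = ((1.960 + 1.2816) / atanh(0.6))² + 3 = (3.2415 / 0.6931)² + 3 = 24.87, so 25.

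This does not reproduce 30, and the broken sentence does not allow the calculation to be rebuilt. The difference is in the safe direction: at n = 30 the power is Φ(0.6931 × √27 − 1.960) = Φ(1.64) ≈ 95%. It has no bearing on multiplicity.

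**2. False-positive rate under three readings.** Suppose PBR is unrelated to severity. The two test statistics are then approximately bivariate normal with correlation ρ.

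- Each score as its own result: 5% each, whatever ρ is.
- Either score suffices: P(|Z₁| > 1.96 or |Z₂| > 1.96). At ρ = 0 this is 1 − 0.95² = 9.75%.
- Both scores required: 0.05 + 0.05 − P(either).

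| ρ (assumed) | Either score | Either score, simulated at n = 30 | Both scores |
|---|---|---|---|
| 0 | 9.75% | 9.7% | 0.25% |
| 0.3 | 9.51% | 9.5% | 0.49% |
| 0.5 | 9.07% | 9.2% | 0.93% |
| 0.7 | 8.35% | 8.2% | 1.65% |
| 0.9 | 7.04% | 7.1% | 2.96% |

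The simulation used 200,000 replicates per row and Pearson t-tests. The 7% to 10% range is therefore correct for the either-score rule. Its upper end needs two severity scores that are nearly uncorrelated.

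**3. Which reading does the plan adopt?** None explicitly. The text says that PBR was correlated with each measure and that a 95% interval was given. It has no sentence on when the severity hypothesis counts as confirmed. The result runs from 0.25% to 9.75% depending on a rule that the reader supplies.

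**4. What adjustment would do.** With Holm, the smaller p-value is compared with 0.025. The either-score rate falls to 4.9% at ρ = 0 and 3.6% at ρ = 0.9. Power at r = 0.6 and n = 30 for that first step is Φ(3.602 − 2.241) = Φ(1.36) ≈ 91%. The correlation detectable with 90% power moves from tanh(3.2415/√27) = 0.55 to tanh((2.241 + 1.2816)/√27) = 0.59. The cost is small, so the case against a change does not rest on lost power.

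**5. Septic shock.** The ROC analysis ("To assess the ability of PBRs (sensitivity and specificity) to predict septic shock") is presented as prediction, and no test of the area under the curve is stated. Counting it as a third test of the hypothesis would add something the plan does not contain, so no figure is given for it.

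**The case for a change.** The strongest case for a change is that this is not purely descriptive work. The authors state a hypothesis, a type I error of 0.05, a power of 0.9 and a significance rule. A type I error should belong to an identified test, and here it does not. Two scores measuring one construct are the textbook setting in which success on either is reported as success. The significance sentence speaks of differences, but a 95% interval for a correlation that excludes zero is in effect the same 0.05 test, so that wording is no escape. The adjustment would also keep power above the plan's own 0.9.

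Much of this stands. The arithmetic is right, no primary score is named in the available text, and a sentence on discordant scores would have helped. What does not stand is the step from that omission to an inflated error rate in the plan. The plan promises no familywise control, and it does not say that one significant score is enough. The place where a primary correlation might have been named is also the place where the text is damaged, so its absence cannot be asserted firmly.

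The remedy is weaker than it looks. The section is written in the past tense, as if the analyses had already been done. If so, naming a primary score or adopting Holm now would not be prespecification, and what remains is a label on the results.

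**Conclusion.** No change to the plan is needed. Followed as written, it gives two severity correlations, each with its own 95% interval and its own valid 5% test. Both scores are named in the plan, so omitting one from the report would be visible. For a single-centre observational study with a descriptive aim, reasonable statisticians differ on adjusting across two named measures of one construct.

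The 7% to 10% figure is conditional. It assumes two-sided tests at 0.05, no true relation between PBR and severity, a correlation between the scores of 0 to 0.9, and an author who accepts significance on either score as confirmation. The last assumption is neither stated nor excluded by the document.

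Sensible reporting fills the gap: give both correlations with their intervals whatever they show, do not present one significant score as confirming the hypothesis, and describe the analyses as exploratory if no rule was set before the data were seen.
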